STUDY PROTOCOL PLAN AND STADISTICAL ANALYSIS PLAN (SAP)

UNIVERSITY CEU CARDENAL HERRERA

Principal investigator: [name] [name]

TITLE: Second-generation Radiofrequency Application and Specific Therapeutic Exercise as a Treatment for Stress Urinary Incontinence Due to Urethral Instability. Randomised Clinical Trial

Research and Ethics Committee of CARDENAL HERRERA CEU UNIVERSITY:
CEEI25/646

NCT ID:

DATE: 01-14-2026

STUDY PROTOCOL PLAN

Objectives:

The objectives of our study have been the following:

The purpose of this study is to evaluate the correlation between urethral instability, assessed by ultrasound analysis of the bladder neck opening, and the severity of SUI, assessed by validated standard questionnaires. The determination of standard ultrasound parameters that allow urethral instability to be related to the severity of SUI would be a valuable finding for accurately diagnosing the severity of SUI using low-cost, easy-to-use imaging methods.

A randomized, single-blind clinical trial will be conducted in women with stress urinary incontinence (SUI). Participants will be randomly assigned to one of three intervention groups: radiofrequency (RF), specific pelvic floor muscle exercise (PFMT), or combined treatment (RF + PFMT). The study will be carried out at Clínica Traña (San José, Costa Rica), with an expected start date in 2025. The study will adhere to the principles of the Declaration of Helsinki and current European data protection regulations.

Adult women with urinary leakage and a bladder neck opening greater than 90°, assessed by functional ultrasound, will be included. Women with other pelvic floor disorders, pregnancy, recent treatments (RF, PFME, hormonal or laser therapies), relevant neurological, metabolic, or cardiovascular conditions, prior pelvic surgery, active infections, or contraindications to the interventions will be excluded. The estimated sample size is 117 participants (39 per group), calculated to detect statistically significant differences with 80% power and a 5% significance level, allowing for a 30% dropout rate.

Before the intervention, all participants will undergo physical examination, digital palpation, and functional pelvic floor ultrasound, as well as complete validated questionnaires assessing urinary incontinence severity and quality of life (ICIQ-SF, King's Health Questionnaire, and Sandvik Severity Index). These assessments will be repeated at the end of the intervention and at 15 days, 3 months, 6 months, and 12 months post-intervention.

Randomization will be performed using statistical software, and outcome assessors will remain blinded to group allocation. Data will be coded and securely stored, ensuring participant confidentiality in accordance with the General Data Protection Regulation (EU 2016/679).

The RF intervention will consist of five weekly sessions of non-ablative fractional vaginal radiofrequency with temperature control and standardized parameters. The PFME program will comprise a structured core and pelvic floor exercise protocol supervised by physiotherapists, conducted twice weekly over a 16-week period. The combined group will receive both interventions.

Primary outcomes will include pelvic floor muscle strength and function (Oxford scale, endurance, and fatigability), ultrasound parameters (bladder neck opening, urethral hypermobility, and presence of prolapse), and validated questionnaires assessing urinary incontinence severity and quality of life.

Statistical Analysis Plan (SAP)

Data will be expressed as mean \pm standard deviation or as a percentage. The distribution of the sample will be determined using the Kolmogorov-Smirnov test. For quantitative variables, depending on the type of variable, Student's t-test or Mann-Whitney U test will be performed. The correlation between variables will be analyzed using Spearman's correlation. In the case of qualitative variables, the association between variables will be analyzed using bivariate or multivariate logistic regression, as appropriate, and contingency tables. The statistical significance of the difference between them will be evaluated using Pearson's χ^2 test. Statistical significance will be assumed with p-values <0.05 .

To evaluate the diagnostic capacity of bladder neck opening measured by ultrasound analysis in the classification of the severity of stress urinary incontinence, a logistic regression analysis was performed. The dichotomized severity of the Sandvick test (mild/moderate versus severe/very severe) will be taken as the gold standard. Demographic and clinical variables will be evaluated as possible covariates and included in subsequent models if they had a p-value < 0.200 .

Sensitivity, specificity, Youden's index (sensitivity + specificity - 1), and positive and negative likelihood ratios (LR+ and LR-) will be calculated for bladder neck opening at rest, during the Valsalva maneuver, the variation between the two, and for the maximum model with the three variables.

The optimal cutoff point for bladder neck opening at rest will be determined using the Youden index. Subsequently, this value will be transformed into clinical units (mm) by algebraic solving of the logistic model equation, adjusted for relevant covariates (age and BMI). This approach preserves the statistical fit of the model while providing a clinically interpretable threshold.

Studentized residuals, leverage values, and Cook's distances will be estimated to identify possible outliers and influential values in the dependent variable, the predictors, and the model as a whole.

Receiver operating characteristic (ROC) curves will be constructed to determine the area under the curve (AUC). Likewise, the Hosmer-Lemeshow goodness-of-fit test will be applied to compare the observed and expected frequencies of the model (considering $p > 0.05$ as an adequate fit). The accuracy of the probabilistic predictions will be evaluated using the Brier Score (lower values indicate better performance). The

analysis will be performed using SPSS Statistics 29.0 (IBM Corp.)

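### The Objectives state only an ultrasound–severity correlation; the treatment comparison implied by the title, the three randomised arms and the per-group sample size is specified nowhere.

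*Combined protocol and SAP*

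**What the plan says.** The title describes "Specific Therapeutic Exercise as a Treatment for Stress Urinary Incontinence Due to Urethral Instability. Randomised Clinical Trial".

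Under Objectives, the single stated purpose begins "The purpose of this study is to evaluate the correlation between urethral instability" and pairs it with SUI severity, instability being read from the bladder neck opening on ultrasound. The reason given is diagnostic: ultrasound parameters that track severity would be a cheap and simple tool. The sentence names no treatment, no arm and no visit.

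The next paragraph describes the design: "Participants will be randomly assigned to one of three intervention groups", namely radiofrequency (RF), pelvic floor exercise (PFMT) or both. The paragraph after that gives 117 women, 39 per group, "calculated to detect statistically significant differences with 80% power and a 5% significance level", with allowance for 30% dropout.

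The outcome text lists muscle function, ultrasound parameters and questionnaires together as primary. They are measured before the intervention, at its end, and at 15 days, 3, 6 and 12 months afterwards.

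The SAP's first paragraph names Student's t-test, Mann-Whitney, Spearman correlation, logistic regression and Pearson's chi-square, with p<0.05 for significance. It does not mention the randomised groups. The rest of the SAP sets out a logistic and ROC analysis of bladder neck opening against dichotomised Sandvik severity.

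**The concern.** The objective and the design answer different questions. A correlation between an ultrasound measurement and a severity score does not need randomisation. Whether RF, exercise or the combination works better does need it, and that question appears in the title and the design but not in the Objectives or the SAP.

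This matters in two ways. First, any statement about treatment would depend on which arms, outcome and visit were picked once results were available. A favourable result could not be told apart from a selected one, and a null result could not be read against any planned effect. Second, the power statement refers to differences, while the stated objective contains no difference to detect. A reader cannot tell what the 117 women were meant to show.

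**Working it through.** **1. Placing the passages side by side.**

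| Element | Question it serves | What is specified |
|---|---|---|
| Objectives | Correlation with severity | Two variables; no visit |
| Title, randomisation | Treatment | Three arms; no hypothesis |
| Sample size | Differences, per group | 80%, 5%, 30% dropout; no outcome, contrast, effect size or SD |
| Primary outcomes | Not stated | Several domains; no single outcome or visit |
| SAP, first paragraph | Not stated | Generic tests; arms not mentioned |
| Rest of SAP | Diagnostic | Reference standard, covariate screen, cut-off rule, fit measures |

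The diagnostic question has a full analysis. The treatment question has none.

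**2. Choices left open.** Three arms give 3 pairwise contrasts. The visits after baseline are 5 (end of intervention, 15 days, 3, 6 and 12 months). That is 3 × 5 = 15 candidate comparisons per outcome. The primary list names six measures (Oxford scale, endurance, fatigability, bladder neck opening, urethral hypermobility, prolapse), and three questionnaires are named among the assessments. Over nine measures, 15 × 9 = 135. This counts open choices; it is not an error rate.

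**3. Can 117 be reproduced?** Only the dropout step can be examined, and it fits two readings:
- Dividing by retention: 27 / 0.70 = 38.6, rounded up to 39.
- Multiplying up: 30 × 1.30 = 39.

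So the plan implies 27 or 30 completers per arm. The calculation behind those figures cannot be recovered, because no effect size, SD or contrast is given.

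**4. Detectable treatment difference** (assumed: two-sided 5%, 80% power, one pairwise contrast). The normal approximation is d = (1.96 + 0.84) × √(2/n).
- n = 27: 2.80 × √(2/27) = 0.76; exact t calculation 0.78.
- n = 30: 2.80 × √(2/30) = 0.72; exact t calculation 0.74.

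With alpha split over two contrasts (0.025 each), the multiplier is 2.24 + 0.84 = 3.08.
- n = 27: 0.84; exact t 0.86.
- n = 30: 0.80; exact t 0.81.

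**5. Detectable correlation** (assumed: two-sided 5%, 80% power, Fisher z for a Pearson coefficient; the SAP specifies Spearman). r = tanh(2.80 / √(N − 3)).
- N = 81 (3 × 27): tanh(2.80 / √78) = 0.31.
- N = 90 (3 × 30): tanh(2.80 / √87) = 0.29.
- N = 117: tanh(2.80 / √114) = 0.26.

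The same sample thus corresponds to quite different targets depending on the question, and the documents name none of them.

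**The case against.** The strongest reply is that a treatment comparison is plainly intended. The primary outcomes are ones that treatment could change, assessors are blinded to allocation, the sample size is per group, and the SAP names tests that compare groups. That stands as evidence of intent. It does not settle the contrast, the outcome or the visit, and the tests named for quantitative variables compare two groups while the trial has three.

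Three stronger readings are tempting, and the text does not support them:
- *The stated purpose is cross-sectional.* A reader might infer this because ultrasound and questionnaires are both collected before the intervention. No visit is given, though, and both are repeated at five later visits, so a correlation across visits or of changes is equally open.
- *The sample size was calculated for treatment differences.* The per-group figure points that way, but the statement does not say what differs or between whom.
- *A single detectable effect follows from 39 per group.* It does not: the dropout formula and the sidedness of the test are unstated, so only a range can be given.

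It is also fair to say that multiple primary outcomes and repeated visits raise a multiplicity issue in their own right. They are counted here only to show how much is left open when no objective fixes the comparison.

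**Conclusion.** The point holds in this form: the Objectives state a correlation with no visit, and the treatment comparison that the title, the randomisation and the per-group sample size imply is specified in no objective, hypothesis or SAP sentence. The power statement names no outcome, contrast or effect size. As written, the plan leaves 15 candidate comparisons per primary outcome, each at p<0.05, from which a treatment conclusion could be drawn after the fact.

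The detectable effects describe what 117 women could show, not what the sponsor planned. They rest on the assumptions stated with each calculation. The finding itself rests on the text and does not depend on them. It should be corrected before the analysis of treatment begins; confidence is moderate, because the intent to compare arms is evident even though it is not written down.

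**What to change.** - **Add a primary objective** that is a randomised comparison between arms on one named outcome and visit already in the schedule, for example ICIQ-SF at 12 months.
- **Name the contrast or contrasts.** This is the sponsor's choice. Examples are the combined arm against each single-treatment arm, or a three-arm global test followed by pairwise tests. If there is more than one, state the alpha rule.
- **List the correlation and cut-off work as a separate objective** and say which visit it uses.
- **Restate the power** for the chosen comparison at N = 117, giving the outcome, SD, sidedness and dropout formula. The present statement cannot simply be attached to the new objective, because it has no effect size behind it.

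**Cost.** Wording in the protocol and SAP plus one power calculation. No new data or patients are needed if the detectable effect is restated. The downside is a less favourable figure if alpha is split. Keeping the smaller effect as the target instead would need more women: with 27 completers per arm, power for d = 0.78 falls from 80% to about 71% at 0.025, and restoring 80% takes about 33 completers. Dividing by retention, 33 / 0.70 = 47.1, rounded up to 48 randomised per arm, or 144 in all.

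### Entry requires a bladder neck opening above 90°, so the correlation, AUC and cut-off for bladder neck opening describe only those women and do not support the general diagnostic aim

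*Combined protocol and SAP*

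**What the plan says.** Under Objectives, the protocol states its purpose: to "evaluate the correlation between urethral instability, assessed by ultrasound analysis of the bladder neck opening, and the severity of SUI". The hoped-for use is "accurately diagnosing the severity of SUI using low-cost, easy-to-use imaging methods", with no restriction to women whose opening is wide.

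The eligibility paragraph under the same heading admits adult women who leak urine and have a "bladder neck opening greater than 90°, assessed by functional ultrasound". It does not say whether the 90° is measured at rest or on Valsalva.

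The SAP returns to the diagnostic aim: "To evaluate the diagnostic capacity of bladder neck opening measured by ultrasound analysis" in classifying severity. On the reference standard it says: "The dichotomized severity of the Sandvick test (mild/moderate versus severe/very severe) will be taken as the gold standard". Sensitivity, specificity, Youden's index and likelihood ratios are planned for "bladder neck opening at rest, during the Valsalva maneuver, the variation between the two, and for the maximum model with the three variables", and ROC curves with AUC are added. The Youden cut-off for the opening at rest is then expressed in mm after adjustment for age and BMI. Spearman's method is named for correlations.

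The documents describe no cohort other than the trial population, no analysis of screened women at or below 90°, no correction for range restriction and no limit on the diagnostic conclusion.

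**The concern.** The ultrasound parameter under evaluation also decides who is studied. Women with smaller openings never reach the correlation, ROC or cut-off analysis. Correlation and AUC both depend on how widely the predictor varies in the sample, so removing one end of its range makes a given underlying relation look weaker. The Youden point is also found within whatever range remains.

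At stake is the only purpose the Objectives section states. A measurement that separates mild from severe SUI reasonably well could be reported as weak, and a cut-off could be published for SUI in general that reflects the entry rule as much as the disease.

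**Working it through.** **Plan's own figure.** None exists for this objective: no expected AUC, correlation, precision or share of women below 90° is given. The stated 117 (3 × 39) concerns the randomised comparison and does not bear on this point.

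**From the documents.** Entry above 90°; opening at rest, on Valsalva and their difference as index measures; dichotomised Sandvik severity as reference; cut-off chosen by Youden's index within the sample.

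**Assumed.** Opening X and latent severity S are standard bivariate normal with correlation ρ, and a woman is severe if S exceeds the point that leaves 35% (or 40%) above it. The lowest 5% to 75% are excluded. Selection is either direct (on X) or indirect (on a second measure correlated 0.6 with X and related to severity only through X). Each scenario used 1,000,000 simulated women. Covariates were not modelled.

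**Hand check, ρ = 0.5.**
- Unselected Spearman = (6/π)·arcsin(ρ/2) = 1.910 × 0.2527 = 0.48, as simulated.
- If half are excluded directly, the variance of X becomes 1 − 2/π = 0.363, so its SD ratio is u = 0.603. The Pearson correlation becomes ρu/√(1 − ρ² + ρ²u²) = 0.301/√(0.75 + 0.091) = 0.33. The simulated Spearman is 0.31.

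**Correlation and AUC, ρ = 0.5, 35% severe.** Spearman here uses continuous latent severity, so it is only indicative for a graded questionnaire.

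| Excluded | Spearman, direct | AUC, direct | Spearman, indirect | AUC, indirect |
|---|---|---|---|---|
| 0% | 0.48 | 0.734 | 0.48 | 0.734 |
| 5% | – | 0.718 | – | – |
| 10% | 0.42 | 0.706 | 0.46 | – |
| 25% | 0.37 | 0.678 | 0.45 | 0.715 |
| 50% | 0.31 | 0.643 | 0.43 | 0.707 |
| 75% | 0.25 | 0.615 | 0.42 | 0.701 |

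AUC loss, direct: 0.734 − 0.718 = 0.016 at 5%, 0.734 − 0.706 = 0.028 at 10%, and 0.734 − 0.615 = 0.119 at 75%. Indirect: 0.734 − 0.715 = 0.019 at 25% and 0.734 − 0.701 = 0.033 at 75%.

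**Other correlations (40% severe, direct).** With ρ = 0.3, AUC 0.637 falls to 0.618 (10% excluded) or 0.580 (50%). With ρ = 0.7, AUC 0.831 falls to 0.804 or 0.719.

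**Youden cut-off re-derived in the selected sample, ρ = 0.5, 40% severe.** The cut-off is in SD of X.

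| Selection | Excluded | Cut-off | Sensitivity | Specificity | Logistic slope |
|---|---|---|---|---|---|
| None | 0% | 0.06 | 0.68 | 0.66 | 0.96 |
| Direct | 25% | 0.43 | 0.58 | 0.68 | 0.93 |
| Direct | 50% | 0.79 | 0.53 | 0.68 | 0.94 |
| Direct | 75% | 1.25 | 0.48 | 0.69 | 0.95 |
| Indirect | 25% | 0.25 | 0.67 | 0.64 | 0.94 |
| Indirect | 50% | 0.47 | 0.65 | 0.65 | 0.95 |
| Indirect | 75% | 0.74 | 0.64 | 0.65 | 0.94 |

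With 35% severe and direct selection, sensitivity goes from 0.68 to 0.60, 0.54 and 0.49, and specificity from 0.66 to 0.66, 0.67 and 0.68. Under indirect selection the AUC hardly drops, but the cut-off still rises clearly.

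**The case against.** **The two measurements may differ.** Entry is an angle in degrees, state unspecified. The planned cut-off is for the opening at rest, in mm. If entry is judged on Valsalva, or if the mm value is a distance, women with small resting values do enter and truncation is indirect. This stands. It reduces the expected AUC loss to about 0.02–0.03 under the assumed correlation of 0.6, but does not remove the shift in the cut-off.

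**The excluded share may be small.** The title concerns SUI due to urethral instability, and few referred women may fall at or below 90°. The documents cannot settle this, so the mild scenarios belong beside the severe ones.

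**For women above 90° nothing is biased.** The estimates are valid for that group, and the entry rule may suit the randomised comparison. This also stands. The difficulty arises only because the Objectives section claims diagnosis of SUI severity without that restriction. It is a limit on the population to which the results apply.

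**Collecting data on screen failures may not be simple.** The documents do not say whether an eligibility scan records both rest and Valsalva. The expected start was 2025 and the document is dated 01-14-2026, so some women may already have been screened out. Both points limit the preferred remedy but do not affect the restriction of the claim.

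**Conclusion.** The point holds as a mismatch between the general diagnostic aim and the selected sample. In every scenario run, selection lowered Spearman, AUC and sensitivity at the within-sample Youden cut-off, and raised that cut-off. With a latent correlation of 0.5 and 35% severe, the AUC loss runs from about 0.02 (5% excluded directly) to 0.12 (75%), and is 0.02–0.03 under indirect selection with 25–75% excluded. These sizes rest on assumed normality, prevalence and correlations. The rest-to-Valsalva difference was not modelled separately.

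Three stronger readings are not supported:

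- **That specificity is badly distorted.** At the unselected population's cut-off it would fall from 0.66 to 0.47 or 0.07 (25% or 50% excluded directly; correlation 0.5, 40% severe). The SAP instead derives the cut-off within the sample, where specificity stays near 0.64–0.69. The logistic slope is also little changed.
- **That no threshold at or below the entry value can be found.** This is true only for the measure used for entry, and the documents do not show that it is the resting measure for which the cut-off is derived.
- **That a large loss of accuracy is certain.** The share of women at or below 90° is not given, so the loss may be small.

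**What to change.** 1. State once which measurement the 90° criterion uses (rest or Valsalva) and in what unit, and reconcile it with the resting cut-off in mm in the SAP. Cost: text only.
2. State that the correlation, AUC, sensitivity, specificity, likelihood ratios and cut-off apply only to women with SUI and an opening above 90°, and drop the general diagnostic claim from the Objectives. Cost: text only.
3. Preferably, for women still to be screened who have stress leakage and meet all other criteria, collect Sandvik and ICIQ-SF before the 90° decision. Run the diagnostic analyses in all of these women and randomise only those above 90°, so that randomisation is untouched. The general claim in item 2 could then be kept for that wider group. Cost: consent and ethics wording, and two short questionnaires for screen failures. It works only if the eligibility scan records both rest and Valsalva. If it does not, or if women already screened out cannot be recovered, item 2 applies.

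### The plan has no systematic recording or analysis of harms, and the first scheduled post-baseline assessment comes after all five radiofrequency sessions in both arms that receive them

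*Combined protocol and SAP*

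**What the plan says.** The Study Protocol Plan randomises women to RF, exercise, or both, with 39 per group. It describes the treatments as follows.

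- RF: "The RF intervention will consist of five weekly sessions of non-ablative fractional vaginal radiofrequency with temperature control and standardized parameters".
- Exercise: a supervised programme, "conducted twice weekly over a 16-week period".
- Combined arm: "The combined group will receive both interventions". Neither the order nor the overlap of the two treatments is given.

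On assessments it says: "Before the intervention, all participants will undergo physical examination, digital palpation, and functional pelvic floor ultrasound", together with three questionnaires on incontinence severity and quality of life. On timing: "These assessments will be repeated at the end of the intervention and at 15 days, 3 months, 6 months, and 12 months post-intervention". Nothing is scheduled between baseline and the end of the intervention.

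On outcomes: "Primary outcomes will include pelvic floor muscle strength and function (Oxford scale, endurance, and fatigability), ultrasound parameters", and then the questionnaires. No secondary outcomes are listed.

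The Statistical Analysis Plan covers group tests, correlation, logistic regression and the diagnostic performance of bladder neck opening. It has no safety analysis.

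**The concern.** A trial that sets repeated vaginal heating against exercise, and against the two together, will be read for tolerability as well as benefit. Followed as written, this plan produces no graded, dated and attributed record of harm in any arm. It could conclude in favour of RF or the combination on efficacy data alone.

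Timing adds to the problem. A transient reaction after one of the early RF sessions has no scheduled assessment near it. In the combined arm the first assessment may come weeks after the last RF session, so the two RF arms may be examined at different distances from the exposure.

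Withdrawal is a third gap. The plan allows for 30% dropout but does not provide for recording why a woman left. Someone who stopped because she could not tolerate treatment would look like any other loss to follow-up. Data of this kind cannot be reconstructed reliably once the sessions are over.

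**Working it through.** The plan states no figure about harm, so there is none to reproduce. The check compares the schedule with the lists of assessments and outcomes, then asks what systematic recording could show at the planned size.

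**Inputs** (all from the Study Protocol Plan): 3 arms × 39 = 117 women; 5 weekly RF sessions; exercise twice a week for 16 weeks; first repeat assessment when the intervention ends; 30% dropout allowance.

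**1. Is any harm measure planned?**

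| Element | Content | Harm measure |
|---|---|---|
| Assessments | Physical examination, palpation, ultrasound, three questionnaires | None named |
| Outcomes | Muscle strength and function, ultrasound parameters, questionnaires | None named |
| SAP | Group tests, correlation, logistic regression, diagnostic accuracy | No safety analysis |

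The text has four safety-related elements: exclusion of women with contraindications, temperature control on the device, supervision of the exercise, and the repeated examination. None is tied to recording harm. Presence of prolapse is listed as an ultrasound parameter, not as a harm of heating.

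**2. When is the first post-baseline assessment?** With session 1 at week 0, session 5 falls at week 4.

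- RF arm: the assessment follows session 5.
- Combined arm, both treatments starting together (an assumption): 16 − 4 = 12 weeks after the last RF session, or 16 − 5 = 11 if RF is counted as filling five weeks.
- Combined arm, RF finished before exercise starts: about 16 weeks.
- Combined arm, RF given last: about 0 weeks.

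Under every ordering the assessment comes after all five RF sessions. Only the length of the gap depends on the ordering.

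**3. How much exposure is involved?** RF is assigned to 2 × 39 = 78 women, which is 78 × 5 = 390 planned RF sessions (195 per arm). Planned contacts per woman are 5 in the RF arm and 2 × 16 = 32 in the exercise arm. In the combined arm they number up to 5 + 32 = 37. A 30% dropout is 0.30 × 39 = 11.7, or about 12 women per arm, with no planned record of the reason.

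**4. What could systematic recording show?** Count each woman once, as having at least one event or none. With zero events in n women, the one-sided 95% upper limit on the true proportion is 1 − 0.05^(1/n), and the upper end of the two-sided 95% exact interval is 1 − 0.025^(1/n).

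| | n | One-sided 95% limit | Upper end, two-sided 95% |
|---|---|---|---|
| One RF arm | 39 | 7.4% | 9.0% |
| Both RF arms | 78 | 3.8% | 4.6% |

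The chance of seeing at least one affected woman is 1 − (1 − p)^n. For illustrative true rates, which the documents do not give:

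- p = 2%: 54.5% with 39 women, 79.3% with 78.
- p = 5%: 86.5% with 39 women, 98.2% with 78.

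**The case against.** The strongest reply is that the absence of a written harm outcome does not make the trial blind to harm. The outcome sentence is not worded as a closed list. Women in the RF arms return weekly for treatment, and those doing exercise attend twice weekly, so staff will see them and may hear complaints. The physical examination is repeated at every follow-up visit and could show a persisting lesion. The device is temperature-controlled, and a log that goes unmentioned may still exist.

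Much of this stands, and it limits what can be said. A reader might infer that the trial cannot report harms at all, or that early RF reactions will have resolved before anyone looks. The documents support neither. Contact during treatment is frequent, and nothing in the text says how long such reactions last. A reader might also take a gap of 11 or 12 weeks in the combined arm as settled; it rests on a concurrent start that the plan does not state. If RF is given last, the difference in gap between the RF arms largely disappears. Nor does the text show that delivered temperature goes unrecorded, only that recording it is not mentioned.

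It is also fair to note that the stated objective and most of the SAP concern the diagnostic link between bladder neck opening and severity, and that the SAP names no specific contrast between arms. The title, the randomisation and the outcomes nevertheless imply a treatment comparison.

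What the reply does not meet is the central point. Incidental notes and a late examination do not give harm counts that are graded, attributed and comparable between arms.

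**Conclusion.** The concern holds in this form: no systematic recording or analysis of harm is planned in any arm, and no post-baseline assessment is scheduled until all five RF sessions are over in the two RF arms. Both statements hold whatever the order of treatments in the combined arm. The interval there, about 0 to 16 weeks, depends on an order the plan leaves open.

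The consequence is that short-lived events across 390 planned RF sessions may go unrecorded, and the trial would have no planned basis for comparing harm between RF, exercise and the combination. The efficacy estimates are not affected, so this is something the sponsor should correct, not a flaw that invalidates the trial.

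For any statement about RF alone or the combination, the relevant zero-event limit is the per-arm 7.4%. The 3.8% applies only if the two RF arms are pooled, which treats the risk as the same with and without exercise. Both limits assume that all women assigned RF receive at least one session. Women who leave later stay in the denominator, though with less exposure.

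**What to change.** Add a secondary safety outcome to the Study Protocol Plan and a matching paragraph to the SAP.

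- **Recording.** Whoever delivers each RF or exercise session completes a standard form: event type, severity, relation to RF or to exercise, date, and whether the session was completed. The role is worded this way because the plan names physiotherapists only for the exercise. Use the same form at every follow-up visit.
- **Withdrawal and exposure.** Record the reason for each withdrawal and, where the device provides it, the delivered temperature at each RF session.
- **Schedule.** State the order and overlap of the two treatments in the combined arm, so that the time from last RF session to first assessment is known.
- **Analysis.** Report the number and proportion of women with each type of event by arm, with exact confidence intervals, in all women who received at least one session. Also report RF-related events per RF session, because planned contacts differ widely by arm (5 against 32 or more) and more contacts mean more chances to report. Sessions within a woman are not independent, so present the per-session rate descriptively.

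This needs no extra participants or visits, and it changes no dose or clinical rule. The cost is a little recording time and one extra table. One practical point: the plan keeps outcome assessors blinded, so at follow-up visits the form should be completed by someone else, or after the efficacy measurements.
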